3.1.6 Clinical Trials

As of the most recent Investigator's Brochure, over 5000 subjects have been enrolled and treated in ongoing durvalumab clinical studies. No studies have been completed or terminated prematurely due to toxicity.

The safety profile of durvalumab as monotherapy and combined with other anticancer agents appears consistent with the pharmacology of the target and other agents in the immune checkpoint inhibitor class. No tumour types appeared to be associated with unique AEs. Immune-related AEs (irAEs), which are important risks of immune checkpoint inhibitors, have been observed with durvalumab and include pneumonitis, hepatitis, diarrhea/colitis and intestinal perforation, endocrinopathies (hypo- and hyperthyroidism, adrenal insufficiency, hypophysitis / hypopituitarism, diabetes insipidus and Type 1 diabetes mellitus), nephritis, rash/dermatitis, pancreatitis, myocarditis, myositis/polymyositis and rare/less frequent irAEs including neuromuscular toxicities such as myasthenia gravis and Guillain-Barre syndrome. Other inflammatory responses that are rare with a potential immune-mediated etiology include, but are not limited to, pericarditis, sarcoidosis, uveitis and other events involving the eye, skin, haematological and rheumatological events. It is possible that events with an inflammatory or immune-mediated mechanism could occur in nearly all organs. Please refer to the most recent version of the Investigator Brochure for incidence.

3.1.7 Pharmaceutical Data - Durvalumab

Supplied:

Supplied as a vial liquid solution containing 500 mg (nominal) durvalumab. The solution contains 50 mg/mL durvalumab, 26 mM histidine/histidine-HCl, 275 mM trehalose dihydrate, 0.02% (w/v) polysorbate 80, at pH 6.0.

Storage:

Durvalumab must be stored at 2°C to 8°C.

Route of Administration:

Intravenous.

Please refer to the CO.26 Pharmacy Manual for additional details.

3.2 Tremelimumab

3.2.1 Name and Chemical Information

Tremelimumab is a human monoclonal antibody of the immunoglobulin G2 (IgG2) subclass that inhibits binding of B7 ligands (B7.1 (CD80) or B7.2 (CD86)) to cytotoxic T lymphocyte-associated antigen 4 (CTLA-4; cluster of differentiation [CD]152).

See the current tremelimumab Investigator Brochure for additional details and the most up to date information.

3.2.2 Chemical Structure

Tremelimumab has an overall molecular weight of approximately 149 kDa including oligosaccharides.

3.2.3 Mechanism of Action

Tremelimumab binds with high affinity and specificity to human CTLA-4, a cell surface receptor expressed primarily on activated T cells. Binding of CTLA-4 to its target ligands (B7.1 and B7.2) on antigen-presenting cells, provides a negative regulatory signal, which limits T-cell activation. Tremelimumab blocks this interaction of B7 ligands with CTLA-4, thus leading to prolongation and enhancement of T-cell activation and expansion. This mechanism is supported by in vitro studies where tremelimumab antagonizes binding of CTLA-4 to B7 ligands and enhances human T-cell activation as demonstrated by increased cytokine (IL-2, IFN- γ) production.

3.2.4 Experimental Antitumour Activity

In a mouse model of fibrosarcoma, an anti-mouse CTLA-4 antibody demonstrated dose-dependent antitumour activity and, at the maximum dose tested, resulted in complete tumour regression in 4 of 5 treated animals. Also these animals were resistant to tumour rechallenge, demonstrating a durable antitumour immunity. Finding was corroborated in other mouse models of cancer.

In a mouse model of colon cancer, the combination of anti-mouse PD-L1 and anti-mouse CTLA-4 resulted in greatly increased activity with tumour regression observed in all mice treated relative to control.

3.2.5 Clinical Trials

To date, 34 clinical studies have been conducted in over 1500 patients in both monotherapy and combination therapy clinical trials. Full details are described in the current tremelimumab Investigator Brochure.

To date, no tumour type or stage appears to be associated with unique AEs (except for vitiligo that appears to be confined to subjects with melanoma). Treatment-related AEs were reported at similar rates in the 10 and 15 mg/kg groups, and were mostly Grade 1 or 2 in severity. The most frequent (in > 5% of subjects) treatment-related AEs (all grades) in patients with tremelimumab monotherapy were diarrhea, rash, pruritus, fatigue, nausea, vomiting, decreased appetite, headache, pyrexia, abdominal pain, and colitis. Please refer to the most recent version of the Investigator Brochure for incidence.

Across clinical trials, a pattern of efficacy has emerged that is similar to the anti-CTLA-4 antibody, ipilimumab, which appears to be consistent across tumour types. Response rates to anti-CTLA-4 antibodies are generally low, approximately 10%. However, in subjects who respond, the responses are generally durable, lasting several months even in subjects with aggressive tumours such as refractory metastatic melanoma.

3.2.6 Pharmaceutical Data - Tremelimumab

Supplied:

Supplied as a vialled solution containing 400 mg (nominal) tremelimumab. The solution contains 20 mg/mL tremelimumab, 20 mM histidine/histidine-HCl, 222 mM trehalose dihydrate, 0.02% (w/v) polysorbate 80, 0.27 mM disodium edetate dehydrate (EDTA), pH 5.5.

Storage:

Tremelimumab must be stored at 2°C to 8°C and must not be frozen. The product should be protected from light when not in use.

Route of Administration:
Intravenous.

Please refer to the CO.26 Pharmacy Manual for additional details.

3.3 Fixed Dosing in Durvalumab and Tremelimumab

A population PK model was developed for durvalumab using monotherapy data from a phase I study (study 1108; N=292; doses= 0.1 to 10 mg/kg Q2W or 15 mg/kg Q3W; solid tumours). Population PK analysis indicated only minor impact of body weight (WT) on PK of durvalumab (coefficient of ≤ 0.5). The impact of body WT-based (10 mg/kg Q2W) and fixed dosing (750 mg Q2W) of durvalumab was evaluated by comparing predicted steady state PK concentrations (5th, median and 95th percentiles) using the population PK model. A fixed dose of 750 mg was selected to approximate 10 mg/kg (based on median body WT of ~75 kg). A total of 1000 patients were simulated using body WT distribution of 40–120 kg. Simulation results demonstrate that body WT-based and fixed dosing regimens yield similar median steady state PK concentrations with slightly less overall between-subject variability with fixed dosing regimen.

Similarly, a population PK model was developed for tremelimumab using data from Phase 1 through Phase 3 (N=654; doses= 0.01 to 15 mg/kg Q4W or Q90D; metastatic melanoma) [Wang et al. 2014]. Population PK model indicated minor impact of body WT on PK of tremelimumab (coefficient of ≤ 0.5). The WT-based (1 mg/kg Q4W) and fixed dosing (75 mg/kg Q4W; based on median body WT of ~75 kg) regimens were compared using predicted PK concentrations (5th, median and 95th percentiles) using population PK model in a simulated population of 1000 patients with body weight distribution of 40 to 120 kg. Similar to durvalumab, simulations indicated that both body WT-based and fixed dosing regimens of tremelimumab yield similar median steady state PK concentrations with slightly less between-subject variability with fixed dosing regimen.

Similar findings have been reported by others [Ng 2006, Wang 2009, Zhang 2012, Narwal 2013]. Wang and colleagues investigated 12 monoclonal antibodies and found that fixed and body size-based dosing perform similarly, with fixed dosing being better for 7 of 12 antibodies. In addition, they investigated 18 therapeutic proteins and peptides and showed that fixed dosing performed better for 12 of 18 in terms of reducing the between-subject variability in pharmacokinetic / pharmacodynamics parameters [Zhang 2012].

A fixed dosing approach is preferred by the prescribing community due to ease of use and reduced dosing errors. Based on average body WT of 75 kg, a fixed dose of 1500 mg Q4W and 75 mg tremelimumab (equivalent to 1 mg/kg) is planned.

Fixed dosing of durvalumab and tremelimumab is recommended only for subjects with > 30 kg body weight due to endotoxin exposure. Patients with a body weight less than or equal to 30 kg should be dosed using a weight-based dosing schedule. This is not expected to be applicable to this trial in an adult patient population.

4.0 STUDY POPULATION

The trial population will consist of patients with advanced (metastatic or locally advanced) histologically confirmed colorectal cancer that is unresectable and who have exhausted standard treatment options. Patients will have progressed with or after standard chemotherapy based regimens containing a fluoropyrimidine, irinotecan and oxaliplatin, or are deemed unsuitable for such regimens by their treating physicians. Subjects with *RAS* wild type tumours must have previously received cetuximab or panitumumab. Subjects treated previously with the following agents will be eligible, though previous treatment with these agents is not a requirement for enrolment:

- anti-VEGF therapy, such as bevacizumab and/or aflibercept and/or regorafenib
- TAS-102

This study is designed to include women and minorities as appropriate, but is not designed to measure differences in intervention effects in these patient populations.

4.1 Eligibility Criteria

There will be NO EXCEPTIONS to eligibility requirements at the time of randomization. Questions about eligibility criteria should be addressed prior to calling for randomization.

The eligibility criteria for this study have been carefully considered. Eligibility criteria are standards used to ensure that patients who enter this study are medically appropriate candidates for this therapy. For the safety of the patients, as well as to ensure that the results of this study can be useful for making treatment decisions regarding other patients with similar diseases, it is important that no exceptions be made to these criteria for admission to the study.

Patients must fulfil all of the following criteria to be eligible for admission to the study:

- 4.1.1 Must have histologically or pathologically confirmed advanced (metastatic or locally advanced) colorectal cancer that is unresectable.
- 4.1.2 Received a prior thymidylate synthase inhibitor (e.g. 5-fluorouracil (5-FU), capecitabine, raltitrexed, UFT) for metastatic disease or as adjuvant therapy. A thymidylate synthase inhibitor may have been given in combination with oxaliplatin or irinotecan.

The intention of this criterion is to ensure that it is the conclusion of the investigator that this patient would not benefit from further therapy with a thymidylate synthase inhibitor and is therefore an appropriate candidate for treatment with best supportive care only.

- 4.1.3 Received and failed an irinotecan -containing regimen (i.e. single-agent or in combination) for treatment of metastatic disease, OR relapsed within 6 months of completion of an irinotecan-containing adjuvant therapy, OR have documented unsuitability for an irinotecan-containing regimen.

Failure is defined as either progression of disease (clinical or radiologic) or intolerance to the irinotecan-containing regimen, where intolerance is defined as discontinuation due to any of the following: severe allergic reaction or delayed recovery from toxicity preventing retreatment.

Documented unsuitability for irinotecan includes (but is not confined to) known hypersensitivity to irinotecan, abnormal glucuronidation of bilirubin, Gilbert's syndrome or previous pelvic/abdominal irradiation.

The intention of this criterion is to ensure that it is the conclusion of the investigator that this patient would not benefit from further therapy with irinotecan and is therefore an appropriate candidate for treatment with best supportive care measures only.

- 4.1.4 Received and failed an oxaliplatin-containing regimen (i.e. single-agent or in combination) for treatment of metastatic disease, OR relapsed within 6 months of completion of an oxaliplatin-containing adjuvant therapy OR have documented unsuitability for an oxaliplatin-containing regimen.

Failure is defined as either progression of disease (clinical or radiological) or intolerance to the oxaliplatin-containing regimen, where intolerance is defined as discontinuation due to any of the following: severe allergic reaction, persistent severe neurotoxicity or delayed recovery from toxicity preventing retreatment.

Documented unsuitability for oxaliplatin includes (but is not confined to) known hypersensitivity to oxaliplatin or other platinum compounds, pre-existing renal impairment, or Grade 2 or greater neurosensory neuropathy.

The intention of this criterion is to ensure that it is the conclusion of the investigator that this patient would not benefit from further therapy with oxaliplatin and is therefore an appropriate candidate for treatment with best supportive care measures only.

- 4.1.5 *For patients with colorectal cancer that is RAS-wild type:*
Received and failed a cetuximab or panitumumab-containing regimen (i.e. single-agent or in combination) for treatment of metastatic disease OR have documented unsuitability for a cetuximab or panitumumab-containing regimen

Failure is defined as either progression of disease (clinical or radiological) or intolerance to the cetuximab- or panitumumab-containing regimen, where intolerance is defined as discontinuation due to any of the following: severe infusion reaction, persistent severe skin toxicity or delayed recovery from toxicity preventing retreatment.

Documented unsuitability for cetuximab includes (but is not confined to) known hypersensitivity to cetuximab or the presence of tumours with an activating *RAS* or *RAF* mutation.

Documented unsuitability for panitumumab includes (but is not confined to) known hypersensitivity to panitumumab or the presence of tumours with an activating *RAS* mutation.

The intention of this criterion is to ensure that it is the conclusion of the investigator that this patient would not benefit from further therapy with either cetuximab or panitumumab and is therefore an appropriate candidate for treatment with best supportive care measures only.

- 4.1.6 Patient prior treatment with VEGF targeting therapy, such as bevacizumab, aflibercept, ramucirumab, or regorafenib, is permitted but not mandatory. Reasons not used are to be documented.

- 4.1.7 Patient prior treatment with TAS-102 (an agent composed of a combination of trifluorothymidine (FTD) and tipiracil hydrochloride (TPI)), is permitted but not mandatory. Reasons not used are to be documented.
- 4.1.8 The only remaining standard available therapy as recommended by the Investigator, in consultation with the patient, is best supportive care.
- 4.1.9 Must have presence of measurable or evaluable disease as defined by Response Evaluation Criteria in Solid Tumours (RECIST 1.1).
- 4.1.10 Imaging investigations including CT/MRI of chest/abdomen/pelvis or other scans as necessary to document all sites of disease done within 28 days prior to randomization.
- 4.1.11 Must have an Eastern Cooperative Oncology Group (ECOG) performance status of 0 or 1.
- 4.1.12 Life expectancy of ≥ 12 weeks at the time of study entry.
- 4.1.13 Must be ≥ 18 years of age. (Note that the lower age limit at each centre will be determined by that centre's policy regarding the age at which an individual may sign their own consent.)
- 4.1.14 Women/men of childbearing potential must have agreed to use a highly effective contraceptive method. A woman is considered to be of "childbearing potential" if she has had menses at any time in the preceding 12 consecutive months. In addition to routine contraceptive methods, "effective contraception" also includes heterosexual celibacy and surgery intended to prevent pregnancy (or with a side-effect of pregnancy prevention) defined as a hysterectomy, bilateral oophorectomy or bilateral tubal ligation, or vasectomy/vasectomized partner. However, if at any point a previously celibate patient chooses to become heterosexually active during the time period for use of contraceptive measures outlined in the protocol, he/she is responsible for beginning contraceptive measures.

Female patients of childbearing potential who are sexually active with a non-sterilized male partner must use at least one highly effective method of contraception while on study and for 6 months after the last dose of durvalumab and tremelimumab or for 3 months after the last dose of durvalumab alone. Male partners of a female subject and non-sterilized male patients who are sexually active with a female partner of childbearing potential must use male condom plus spermicide while on study and for 6 months after the last dose of durvalumab and tremelimumab or for 3 months after the last dose of durvalumab alone. Female partners of a male subject must use a highly effective method of contraception throughout this period. Cessation of birth control after this point should be discussed with a responsible physician. See Section 9.3.1 for additional details.

Women of childbearing potential will have a pregnancy test to determine eligibility as part of the Pre-Study Evaluation (see Sections 5.1 and 5.2); this may include an ultrasound to rule-out pregnancy if a false-positive is suspected. For example, when beta-human chorionic gonadotropin is high and partner is vasectomized, it may be associated with tumour production of hCG, as seen with some cancers. Patient will be considered eligible if an ultrasound is negative for pregnancy.

Male patients should also refrain from donating sperm during the study and for 6 months after the last dose of durvalumab and tremelimumab or for 3 months after the last dose of durvalumab alone.

- 4.1.15 Patient must consent to provision of, and investigator(s) must confirm adequacy of tissue, and confirm access to and agree to submit within 4 weeks of randomization to the CCTG Central Tumour Bank, a representative formalin fixed paraffin block of tumour tissue in order that the specific correlative marker assays proscribed in Section 12 (Correlative Studies) may be conducted. Where adequate amount and quality of tissue exists but local centre regulations prohibit submission of blocks of tumour tissue, the approval of the CCTG must be sought prior to randomization of the first patient to allow cores (two 2 mm cores of tumour from the block) and a predetermined number of slides of representative tumour tissue to be substituted. Failure to submit any tissue samples on request will result in the patient being considered ineligible. Where no previously resected or biopsied tumour tissue exists or is found to be of inadequate amount or quality, additional biopsy of the primary or metastatic tumour will be required for the patient to be considered eligible for the study and will be required to be done prior to randomization. Please refer to the CO.26 Correlative Studies Manual for details concerning adequacy of amount and quality of tumour tissue.
- 4.1.16 Patient must consent to provision of samples of blood in order that the specific correlative marker assays proscribed in Section 12 (Correlative Studies) may be conducted.
- 4.1.17 Patient is able (i.e. sufficiently fluent) and willing to complete the quality of life questionnaires in either English or French. The baseline assessment must be completed within 14 days prior to randomization. Inability (lack of comprehension in English or French, or other equivalent reason such as cognitive issues or lack of competency) to complete the questionnaires will not make the patient ineligible for the study. However, ability but unwillingness to complete the questionnaires will make the patient ineligible.
- 4.1.18 Patients must be accessible for treatment and follow-up. Investigators must assure themselves the patients randomized on this trial will be available for complete documentation of the treatment, adverse events, and follow-up.
- 4.1.19 In accordance with CCTG policy, protocol treatment is to begin within 2 working days of patient randomization.
- 4.1.20 The patient is not receiving therapy in a concurrent clinical study and the patient agrees not to participate in other clinical studies during their participation in this trial while on study treatment.

4.1.21 Adequate normal organ and marrow function as defined below (must be done within 14 days prior to randomization):

| | | |
|------------|---|--|
| Hematology | Absolute neutrophils | $\geq 1.5 \times 10^9/L$ |
| | Platelets | $\geq 100 \times 10^9/L$ |
| | Hemoglobin | $\geq 90 \text{ g/L}$ |
| | Lymphocytes | Note: no range is specified for eligibility |
| Chemistry | Bilirubin | $\leq 1.5 \times \text{ULN}$ (upper limit of normal)* |
| | AST and ALT ** | $\leq 2.5 \times \text{ULN}$ |
| | Serum creatinine or: Creatinine clearance*** | $< 1.25 \times \text{ULN}$ $\geq 40 \text{ mL/min}$ |
| | * If confirmed Gilbert's, eligible providing $\leq 3 \times \text{ULN}$. ** $< 3 \times \text{UNL}$ in presence of liver metastases *** Creatinine clearance to be measured directly by 24 hour urine sampling or as calculated by Cockcroft and Gault equation below: Females: $\text{GFR} = 1.04 \times (140 - \text{age}) \times \text{weight in kg} / \text{serum creatinine in } \mu\text{mol/L}$ Males: $\text{GFR} = 1.23 \times (140 - \text{age}) \times \text{weight in kg} / \text{serum creatinine in } \mu\text{mol/L}$ | |

4.1.22 Patient consent must be appropriately obtained in accordance with applicable local and regulatory requirements. Each patient must sign a consent form prior to enrolment in the trial to document their willingness to participate.

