
5.3 Follow-up for Ineligible Patients

The follow-up requirements for ineligible patients:

- Randomized to **Arm 1** (BSC) include submission of the Baseline Report plus annual follow-up using the Minimal Follow-up Report.
- Randomized to **Arm 2** (tremelimumab and durvalumab) but who have received no protocol therapy include submission of the Baseline Report plus annual follow-up using the Minimal Follow-up Report. Data submission for ineligible participants who have received at least one dose of protocol therapy should be followed according to the protocol to allow for treatment and adverse event assessment.

Note: The dates of objective progression and death must be reported for ineligible patients.

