12.1 Protocol-Mandated Correlative Studies

Archival FFPE Tumour Tissue Submission (Mandatory)

Archival Tumour Block/Slides:

The submission of a representative block of the diagnostic tumour tissue (from primary or metastatic tumour) and the adjacent normal tissue (part of the standard resection) is mandatory for participation on this trial. Blocks will be carefully stored as part of the CCTG Tumour Tissue Data Repository at Queen's University in Kingston, Ontario, but the only assays done will be as part of this study. All patients on whom a diagnostic tumour block is collected will be aware of this retrieval and will have given their consent.

Blocks are the preferred material to collect, as it is well known that tissue materials (including protein and nucleic acid integrity) on unstained sections deteriorate rapidly within 3-6 months after preparation. One of the objectives will be to create tissue micro arrays. These will optimize the amount of tissue available to investigators and permit the preservation of the tumour block submitted.

If, at any time, the submitting hospital requires the block to be returned for medical or legal concerns, it will be returned by courier on request.

Samples will be used for research purposes only and will not be sold. Patients will not be identified by name. The only identification of tissue will be by a patient study number assigned at the time of registration to the trial, the surgical/ histology number and/or patient initials. Material issued to researchers will be anonymized and only identified by a coded number.

Testing specifically for hereditary genetic defects predisposing to malignant disease will not be carried out without the expressed consent of the patient.

Where no previously resected or biopsied tumour tissue exists, additional biopsy of the primary or metastatic tumour will be required.

Directions:

At the same time that the baseline form is submitted, original tumour block should be sent to the CCTG Pathology Coordinator. Centres should contact CCTG if they are unable to submit a tumour block, as sufficient tissue is required for the assays described above.

Within 4 weeks of randomization (note: a request letter will not be sent), complete the EDC Archival Tumour Tissue Submission Form. Print a copy of the completed form and ship tumour blocks/slides along with a Request for Payment form to:

[name]
Pathology Coordinator, Canadian Cancer Trials Group
[name]

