13.3 Sample Size and Duration of Study

The study is designed to have a power of 80% and a two-sided alpha of 10% to detect a 35% reduction in the continuous risk of death (HR 0.65, which corresponds to an increase of median survival from 4.5 to 6.9 months). It is estimated that 150 events will be required to detect this reduction. The final analysis will be performed when 150 events are observed. Assuming an accrual rate of around 10 patients per month, the required number of events would be observed by accruing a total of 180 patients and following them for a minimum of 6 months. The total duration of the trial would be around 24 months.

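### Criterion 4.1.15 lets missing tissue make a patient ineligible after randomization, and Section 5.3 then cuts follow-up on BSC but not for a dosed Arm 2 patient

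*Protocol*

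**What the plan says.** Protocol Section 4.1 fixes when eligibility is judged: "There will be NO EXCEPTIONS to eligibility requirements at the time of randomization". Most of criterion 4.1.15 fits that rule. Before randomization the patient consents, and the investigator confirms that tissue is adequate and accessible and agrees to send it within 4 weeks. Where tissue is absent or inadequate, a biopsy must be done first. The flowsheets in 5.1 and 5.2 make the same split: availability is confirmed before randomization, and shipment follows.

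One sentence of 4.1.15 works differently: "Failure to submit any tissue samples on request will result in the patient being considered ineligible". Section 12.1 repeats the deadline but removes any prompt: "Within 4 weeks of randomization (note: a request letter will not be sent". The documents therefore do not define the moment at which a request has been made and not met.

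Section 5.3 acts on ineligible status however it arose. For BSC patients, and for Arm 2 patients who never received protocol therapy, the requirements "include submission of the Baseline Report plus annual follow-up using the Minimal Follow-up Report". An ineligible Arm 2 patient with at least one dose is followed per protocol, so that treatment and adverse events can be assessed. Section 5.3 also requires progression and death dates for all ineligible patients.

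Two other places bear on this. Section 6.3 follows every randomized patient to death or until told to stop, but refers to Section 4.2 for a rule that is in 5.3. Appendix IV applies follow-up to eligible patients only.

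**The concern.** A block that is not sent after allocation says nothing about whether the patient belonged in the trial. Everything useful for selection has already been checked. The sentence only allows a correctly enrolled patient to be reclassified later, in a trial that the SAP (2.1) describes as open-label.

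The status has arm-dependent consequences. Take two patients whose sites both fail to send tissue. The BSC patient leaves the 8-weekly scans, the 4-weekly visits with adverse event assessment, and the remaining quality-of-life forms. The Arm 2 patient who has had one dose leaves none of them. Ascertainment of the secondary and tertiary endpoints then differs by arm for a reason that arose after randomization.

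**Working it through.** **1. The plan's own figure.** Section 13.3 specifies "a power of 80% and a two-sided alpha of 10" per cent, with "HR 0.65, which corresponds to an increase of median survival from 4.5 to 6.9 months", and puts the requirement at 150 deaths. By Schoenfeld's formula with 2:1 allocation (Section 7.1.1):

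d = (1.645 + 0.842)² / [(2/3)(1/3)(ln 0.65)²] = 6.18 / (0.2222 × 0.1856) ≈ 150.

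The median check is 4.5/0.65 = 6.92 months. Both reproduce. No allowance for ineligibility is stated.

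**2. Overall survival, worst case.** Assume 18 months of uniform accrual, 6 months of minimum follow-up and exponential survival. The expected proportion of BSC patients dead by month 24, with λ = ln 2/4.5 = 0.154, is

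1 − (e^(−6λ) − e^(−24λ))/(18λ) = 1 − (0.397 − 0.025)/2.77 = 0.866, or 51.9 of 60.

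Suppose the deaths of reclassified BSC patients were never recovered, contrary to 5.3. The power is then:

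| BSC reclassified | Patients | Deaths lost | Power |
|---|---|---|---|
| 2% | 1.2 | 1.0 | 79.8% |
| 5% | 3 | 2.6 | 79.4% |
| 10% | 6 | 5.2 | 78.8% |

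Death dates are required and the analysis waits for 150 events, so the planned loss of power is nil.

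**3. Would annual contact find progression?** Under the design exponential, 1 − 0.5^(12/4.5) = 84% of BSC patients die before month 12. For most reclassified BSC patients no annual contact would fall due before death. A progression date would depend on unscheduled imaging.

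**4. PFS.** The simulation inputs were:
- exponential survival with median 4.5 months in both arms (no true effect);
- exponential time to progression with median 2 or 3 months (assumed; the documents give none), independent of survival;
- progression dated at the next 8-weekly scan, 56/30.4375 = 1.84 months apart;
- for reclassified BSC patients, no scans and no progression date, so that the event is death;
- 2:1 allocation, no censoring, Cox model, 1.5 million patients per run.

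| BSC reclassified | PFS HR (Arm 2/BSC), median 2 months | Median 3 months |
|---|---|---|
| 0% | 1.00 | 1.00 |
| 2% | 1.02 | 1.02 |
| 5% | 1.06 | 1.05 |
| 10% | 1.12 | 1.09 |

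BSC progression is dated late, so BSC looks better and the shift is against the experimental arm.

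**5. Other endpoints, from the text.**
- *Response:* all randomized patients are in the denominator. A patient who is not re-imaged cannot have a documented response and counts as a non-responder.
- *Quality of life:* SAP 7.9.4 takes weeks 8 and 16 as primary. Both fall after the 4-week tissue deadline.
- *Adverse events:* events reported on BSC after reclassification are lost. The SAP's All Treated set needs at least one Best Supportive Care Report from a BSC patient, so one reclassified before filing a report also leaves the denominator. A dosed Arm 2 counterpart stays in.

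**The case against.** The strongest reply is that Section 5.3 itself requires progression and death dates, that 6.3 follows everyone to death, and that 13.2 analyses survival by intent to treat. Appendix IV also lists a CT/MRI report, where available, with the Minimal Follow-up Report. This disposes of a reading that some may be tempted to make, that overall survival follow-up is lost by arm. The documents do not support it. For PFS the reply is only partial: requiring a date does not schedule the scan that would establish it.

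Non-submission should also be rare. Adequacy and access are confirmed first, and 12.1 tells centres that cannot send a block to contact CCTG. A reader might infer that tissue arriving after 4 weeks is the trigger. It is not; the trigger is failure to submit on request, which should be less common than lateness. The week-4 visit and form would usually precede reclassification, so it is the later data that are at risk.

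A reader might also take criterion 4.1.19, that "protocol treatment is to begin within 2 working days of patient randomization", as a second post-randomization eligibility test which only Arm 2 can fail. The text does not go that far. Unlike 4.1.15, it names no ineligibility consequence, and Section 7.0 repeats it as a conduct rule. A late starter has been dosed and so keeps full follow-up under 5.3. The SAP tabulates never-treated patients (Tables 1 and 6) apart from ineligible ones (Table 5).

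Finally, 5.3 has a stated reason for following dosed patients fully. That justifies keeping them on schedule; it does not justify taking BSC patients off it because tissue is missing.

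**Conclusion.** The point holds for one sentence in 4.1.15 combined with 5.3. Together they make ascertainment of PFS, response, quality of life and adverse events depend on arm after a site failure that occurs after randomization. Overall survival and the design figures are essentially untouched.

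The PFS shift of about 1.02 to 1.12 rests on assumed reclassification of 2% to 10% of BSC patients, an assumed median time to progression of 2 to 3 months, no true effect, and no scans or progression dates after reclassification. The last assumption is the upper bound for lost ascertainment; any scan actually done reduces the shift. The true rate is unknown from the documents and may be near zero. This is an inexpensive improvement worth making. It does not threaten the primary result.

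**What to change.** In 4.1.15, delete the sentence that turns non-submission into ineligibility and keep the pre-randomization requirements. Record missing tissue as a protocol deviation. In 5.3, state that reduced follow-up can be triggered only by criteria assessable at randomization, so that patients with missing tissue in either arm keep the full assessment schedule. Align Appendix IV with 6.3 so that follow-up covers all randomized patients, and correct the cross-reference in 6.3 from Section 4.2 to 5.3. As housekeeping only, 4.1.19 can leave the eligibility list, since Section 7.0 already contains it.

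SAP 2.1 records that randomization closed on June 29, 2017, so the last 4-week tissue deadline was July 27, 2017. For patients already enrolled, the useful steps are a follow-up clarification under 5.3 and a separate line in SAP Table 5 for ineligibility based on tissue alone.

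The cost is a short wording change and the loss of one sanction that encourages sites to ship tissue; deviation reporting and centre performance monitoring (15.6) remain. The 150 events, 180 patients and 80% power stay as they are.
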